2.3 Rationale for dose and regimen selection

Deferasirox is available in three dosing strengths: 125, 250 and 500 mg for dispersible tablets and 90, 180 and 360 mg for film-coated tablets.

For each patient, the dose is calculated by the physician based on the patient's weight, and then rounded up or down to the nearest tablet configuration, which can result in a variance between the calculated and actual dose of up to 15%. This dosing paradigm is consistent with how deferasirox DT (Exjade[®]) has been developed with regard to safety and efficacy.

All Deferasirox naïve patient or chelation naïve patients or patients who have been treated by other chelators such as Deferiprone (DFP) / Deferoxamine (DFO) or Combination (DFO + DFP) for at least 6 months continuously, at the study entry will use a starting dose of:

- Deferasirox DT of 20 mg/kg/day in transfusion-dependent thalassemia (TDT)
- Deferasirox DT of 10 mg/kg/day in non-transfusion-dependent thalassemia (NTDT),

The equivalent FCT starting dose is:

- Deferasirox FCT of 14 mg/kg/day in transfusion-dependent thalassemia (TDT)
- Deferasirox FCT of 7 mg/kg/day in non-transfusion-dependent thalassemia (NTDT).

For patients with difficulties in swallowing Deferasirox FCT, it is allowed to crush the film-coated tablets. It should be administered by sprinkling the full dose on soft food like yogurt or apple sauce (apple puree). For further instructions, refer to the [Appendix 14](#).

Dose adjustments are permitted as follows:

- Patients receiving the DT formulation: \pm 5-10 mg/kg/day; maximum daily dose: 40 mg/kg/day for TDT patients; 20 mg/kg/day for NTDT patients
- Patients receiving the FCT formulation: \pm 3.5-7 mg/kg/day; maximum daily dose: 28 mg/kg/day for TDT patients; 14 mg/kg/day for NTDT patients.

For ICT naïve patients at study entry the dose can be adjusted after 4 weeks of study treatment and for ICT pre-treated patients, the dose should be adjusted if necessary every 3 months based on serum ferritin levels

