6.1.1 Dosing regimen

Having completed the screening period (including the 5-day wash-out period for patients previously treated with Deferiprone/DFP or Deferoxamine/DFO), eligible patients will start the core phase and be switched on the Day 1 visit to deferasirox DT for 24 weeks followed by deferasirox FCT for 24 weeks duration. Upon completion of Week 48 (Core Phase), the patient can still be treated with deferasirox FCT for a maximum of another 48 weeks or until one of the end of study criteria defined is met, whichever comes first.

The starting dose on Baseline Day 1 would be as following:

- Deferasirox DT of 20 mg/kg/day in transfusion-dependent thalassemia (TDT)
- Deferasirox DT of 10 mg/kg/day in non- transfusion-dependent thalassemia (NTDT),

Table 6-1 Equivalent FCT starting dose at Week 25

Equivalent dose to be used	
Deferasirox DT (mg/kg/day)	Deferasirox FCT (mg/kg/day)
5	3.5
10	7
15	10.5
20	14
25	17.5
30	21

Equivalent dose to be used	
Deferasirox DT (mg/kg/day)	Deferasirox FCT (mg/kg/day)
35	24.5
40	28

All iron chelation pre-treated patients who had received treatment with deferoxamine (DFO) and deferiprone (DFP) will be initiated on deferasirox DT. The dose of deferiprone will be determined by their serum ferritin and the dose of deferoxamine by using the equivalent deferasirox DT dose (see [Appendix 14.2](#)).

Dose adjustment for better treatment effects, based on serum ferritin levels and investigator's judgment, will be allowed for ICT naïve patients after 4 weeks of study treatment and for ICT pre-treated patients every 3 months. The dose adjustments will be performed in steps of 5-10 mg/kg/day for deferasirox DT or in steps of 3.5-7 mg/kg/day for deferasirox FCT.

For each patient the daily dose is calculated by the physician based on the patient's actual body weight, and then rounded up or down to the nearest whole tablet according to the available strengths of deferasirox tablets (125 mg, 250 mg and 500 mg for the DT and 90 mg, 180 mg and 360 mg for the FCT, see [Appendix 14.1](#)).

The investigator should instruct the patient (or legal patient's representative in the case of pediatric patients) to take the study drug as prescribed. All doses planned and prescribed to the patient and all dose changes including reasons for change during the study must be recorded in the eCRF.

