Dose adjustments based on safety are allowed at any time point in the study and will be in increments of 5-10 mg/kg/day for deferasirox DT or 3.5-7 mg/kg/day for deferasirox FCT. Dose adjustments based on efficacy are permitted. For ICT naïve patients at study entry dose adjustments are allowed after 4 weeks of study treatment based on serum ferritin levels and investigator's judgement. For ICT pre-treated patients, the dose of deferasirox should be adjusted if necessary every 3 months based on the trends in serum ferritin and investigator's judgement. For more details please refer to [Table 6.2](#) – Dose of study drug based on serum ferritin level.

Table 6-2 Dose and treatment schedule

Study treatments	Pharmaceutical form and route of administration	Starting Dose* (weeks 1-4)	Dose adjustment (after week 4)	Max dose	Frequency and/or Regimen
Deferasirox DT – TDT patients	Dispersible tablets, p.o.	20 mg/kg/day	+ 5 - 10 mg/kg/day	40 mg/kg/day	Once daily
Deferasirox DT – NTD patients	Dispersible tablets, p.o.	10 mg/kg/day	+ 5 - 10 mg/kg/day	20 mg/kg/day	Once daily
Deferasirox FCT – TDT patients	Film-coated tablets, p.o.	14mg/kg/day	+ 3.5 - 7 mg/kg/day	28 mg/kg/day	Once daily
Deferasirox FCT – NTD patients	Film-coated tablets, p.o.	7 mg/kg/day	+ 3.5 - 7 mg/kg/day	14 mg/kg/day	Once daily

*Iron chelation naïve patients. All iron chelation pre-treated patients see [Section 6.1.1](#) and [Appendix 14.2](#) for guidance.

Table 6-3 Daily dose of study drug based on serum ferritin level

Dose Regimen of Drug for TDT patients	Serum ferritin level
20 mg/Kg Deferasirox DT 14 mg/Kg Deferasirox FCT	1000-1500 ng/ml
30 mg/Kg Deferasirox DT 21 mg/Kg Deferasirox FCT	>1500-2000 ng/ml
40 mg/Kg Deferasirox DT 28 mg/Kg Deferasirox FCT	>2000 ng/ml
Dose Regimen of Drug for NTD patients	Serum ferritin level
5 mg/Kg Deferasirox DT 3.5 mg/Kg Deferasirox FCT	300-799 ng/ml
10 mg/Kg Deferasirox DT	800-2000 ng/ml

Dose Regimen of Drug for TDT patients	Serum ferritin level
7 mg/Kg Deferasirox FCT	
20 mg/Kg Deferasirox DT 14 mg/Kg Deferasirox FCT	>2000 – 4000 ng/ml
30mg/Kg Deferasirox DT 21mg/Kg Deferasirox FCT	>4000ng/mL

Serum ferritin level will be measured monthly to evaluate the study drug response

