7.1.2 Treatment period

The duration of core phase treatment is 48 weeks. Patient visits will occur every 2 weeks during the first month of treatment and then every 4 weeks thereafter until Visit 777 (SEC).

Having completed the screening period (including the 5-day wash out period for patients previously treated with deferiprone (DFO) or deferoxamine (DFP)), patients who are eligible will be enrolled to receive deferasirox DT during 24 weeks then switch to deferasirox FCT for 24 weeks. Daily dose is calculated by the physician based on the patient's actual body weight.

At the start of treatment, iron chelation naïve patients will receive deferasirox DT 10 mg/kg (NTDT patients) or 20 mg/kg (TDT patients) once daily then will transition to the equivalent FCT dose as outlined in the following table.

Table 7-3 Equivalent dose to be used: Deferasirox DT vs Deferasirox FCT

Equivalent dose to be used	
Deferasirox DT (mg/kg/day)	Deferasirox FCT (mg/kg/day)
5	3.5
10	7
15	10.5
20	14
25	17.5
30	21
35	24.5
40	28

All iron chelation pre-treated patients will follow the below guidance:

Patients who were taking deferoxamine (DFO), will need to take the deferasirox DT equivalent deferasirox. For deferiprone (DFP) the dose of deferasirox DT will be based on their serum ferritin. Please refer to [Table 6-2](#).

At the Week 48 visit, patients will roll over to the extension phase in the case that none of the End of Study criteria is met at that time. The patient will receive deferasirox FCT following the same dose regulations and adjustments as per the core phase.

The treatment period of the extension study is approximately 52 weeks (including treatment period (48 weeks), Study Evaluation Completion and 4 weeks Safety Follow-up visits)

For details on study design and dose adjustments, see [Section 4](#) and [Section 6.3](#).

For details of assessments, see [Table 7-1](#) and [Table 7-2](#).

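### NTDT dosing tables list doses above the protocol's own maximum, pre-treated patients have conflicting starting doses, and SAP code S03 can drop correctly dosed patients from the PPS

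*Protocol*

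**What the plan says.** **NTDT maximum.** Section 2.3 gives, for DT, "maximum daily dose: 40 mg/kg/day for TDT patients; 20 mg/kg/day for NTDT patients"; the FCT limit for NTDT is 14 mg/kg/day. Table 6-2 agrees, and Section 6.2.1.3 forbids anything higher. In the same protocol, Tables 6-3 and 14-17 have an NTDT row of 30 mg/kg DT (21 FCT) for ferritin above 4000 ng/ml. Table 14-18 converts prior deferoxamine of 10 to 80 mg/kg/day into 5 to 40 mg/kg DT and does not separate TDT from NTDT.

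**Starting dose.** Section 2.3 includes pre-treated patients: "or Combination (DFO + DFP) for at least 6 months continuously, at the study entry will use a starting dose of" 20 mg/kg DT for TDT or 10 for NTDT. The synopsis gives the same starts by disease type without restriction. So does the list in Section 6.1.1 that opens "The starting dose on Baseline Day 1 would be as following". In Section 7.1.2 it is chelation-naïve "patients will receive deferasirox DT 10 mg/kg (NTDT patients) or 20 mg/kg (TDT patients) once daily", and the Table 6-2 footnote likewise ties these starts to naïve patients. For pre-treated patients, Sections 6.1.1, 7.1.2 and Appendix 14.1 use ferritin after deferiprone and the equivalent dose (half) after deferoxamine.

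**SAP Section 5.5.** These codes all exclude from the PPS:
- S01: starting DT dose not per Table 6-2.
- S03: dose not per Table 6-3.
- S15 and S16: maximum dose not per Table 6-2.
- S17 and S18: adjustment not per Table 6-2.

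S11 and S12, on the size of the adjustment step, keep the patient in every set.

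**The concern.** A site has to pick a dose, and the protocol gives more than one answer. For an NTDT patient with very high ferritin or a high prior deferoxamine dose, a table row points to a dose that Section 6.2.1.3 prohibits. This is a safety matter first. It is not confined to study entry, because ferritin-based adjustment runs through the core phase and, under the same rules, the extension. For pre-treated patients, the start depends on which section the site reads. The combination of deferoxamine and deferiprone is an eligible prior therapy and is named in SAP code S08, but Appendix 14.1, to which S08 points, has no rule for it.

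The statistical consequence is in the PPS. That set is meant to show that the preference result holds in patients treated according to the protocol. If the codes remove patients who were dosed correctly, it no longer does that.

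**Working it through.** No sample-size or power figure is involved. The check compares the dosing tables with each other and with the SAP codes.

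**1. The plan's own conversion.** Appendix 14.1 takes deferoxamine 40 mg/kg/day to 40 / 2 = 20 mg/kg DT and 14 mg/kg FCT (14 / 20 = 0.7). Table 14-18 follows this rule in every row.

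**2. NTDT rows against the maximum of 20 DT (14 FCT).**

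| Source | Rows above the maximum |
|---|---|
| Tables 6-3 and 14-17 | ferritin >4000 ng/ml: 30 DT, 21 FCT (1 of 4 NTDT rows) |
| Table 14-18 | deferoxamine 50, 60, 70, 80: 25, 30, 35, 40 DT (4 of 8 rows) |

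At 50 kg the ferritin row gives 30 × 50 = 1500 mg (Table 14-6), against a permitted 20 × 50 = 1000 mg (Table 14-4). The ratio is 1500 / 1000 = 1.5. For FCT, 21 / 14 = 1.5.

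**3. Starting dose of a pre-treated patient.**
- TDT, 50 kg, after deferiprone, ferritin 2500 ng/ml. Section 2.3 gives 20 mg/kg, or 1000 mg (Table 14-4). Appendix 14.1 gives 40 mg/kg, or 2000 mg (Table 14-8).
- TDT after deferoxamine 20 mg/kg/day. Section 2.3 gives 20 mg/kg; Table 14-18 gives 20 / 2 = 10 mg/kg.

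The fixed start can therefore be half or twice the dose in the appendix.

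**4. Correct naïve DT start (Table 6-2) against S03 read literally (Table 6-3).** The entry limits are ferritin above 1000 ng/ml for TDT and at least 800 for NTDT.

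| Group and ferritin (ng/ml) | Start | Table 6-3 | S03 |
|---|---|---|---|
| TDT 1000–1500 | 20 | 20 | met |
| TDT >1500–2000 | 20 | 30 | failed |
| TDT >2000 | 20 | 40 | failed |
| NTDT 800–2000 | 10 | 10 | met |
| NTDT >2000–4000 | 10 | 20 | failed |
| NTDT >4000 | 10 | 30 | failed |

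The correct start fails in 2 of 3 bands in each group.

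**5. NTDT above 4000 ng/ml, dose set by ferritin.** Any DT dose up to 20 differs from the tabulated 30 and fails S03. Any dose above 20 fails S15. For FCT the pair is S03 and S16, at 14 and 21. Limiting S03 to adjustments does not remove this conflict.

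**6. Adjustment step.** S11 and S12 keep a patient whose step is not 5–10 mg/kg DT or 3.5–7 mg/kg FCT. The adjustment column of Table 6-2 holds those same steps, and S17 and S18 exclude a patient who departs from it. The same deviation is coded both ways.

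**The case against.** The strongest reply is that the text leans towards the maximum. Section 6.2.1.3 calls the ferritin table guidance on suggested doses, subject to the investigator's judgement, and then prohibits doses above 20 mg/kg outright; S15 enforces that limit. So it would be wrong to say that nothing indicates which rule prevails. What remains is that three tables still list prohibited doses without a note, and that S03 treats the suggested doses as a compliance test.

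A second reply is that S03 may be meant for adjustments only, and S01 for naïve patients through the Table 6-2 footnote. Both readings are reasonable. The SAP states neither, and the NTDT conflict above 4000 ng/ml survives both.

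Some stronger readings are tempting and do not hold:
- A reader might take Section 2.3 as the lone outlier, or as the only text that gives the combination a dose. The synopsis and the Day 1 list in Section 6.1.1 are equally unrestricted.
- A reader might use S17 to argue that the permitted step leaves many patients with no dose that avoids exclusion. S11 and S12 keep step deviations, so the codes contradict each other and do not settle it.
- A reader might count every deferoxamine conversion that differs from Table 6-3 as a clash between S08 and S03. S08 covers only patients well managed on prior therapy, so such counts would assume a qualifier that the tables cannot show.

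**Conclusion.** The point stands as a conflict in wording with a safety side and a limited statistical side. The NTDT tables list doses up to 1.5 times (ferritin) and 2 times (40 / 20, deferoxamine 80) the stated maximum. The pre-treated start differs between sections by up to a factor of two in the examples shown. Read literally, S03 fails the correct naïve start in 2 of 3 ferritin bands for TDT and 2 of 3 eligible bands for NTDT. For NTDT above 4000 ng/ml, S03 and S15 cannot both be met.

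This does not put the primary result at risk: SAP Section 2.5.1 uses the FAS, and the PPS analysis is supportive (Section 2.5.4). Nor do the documents show that many patients are affected. They give no distribution of ferritin or prior deferoxamine dose, and the counts above are unweighted table rows. The 2-of-3 figures assume the literal reading of S03.

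The wrong cross-references are editorial: Table 14-17 for 14-18, Table 6-2 for 6-3, and Appendix 14.2 (light meals) for 14.1. So is the phrase "The dose of deferiprone will be determined by their serum ferritin", where the deferasirox dose is meant.

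**What to change.** **Protocol.**
- State in Tables 6-3, 14-17 and 14-18 that the NTDT maximum of 20 mg/kg DT (14 FCT) applies.
- Limit the fixed starts in the synopsis, Section 2.3 and the Section 6.1.1 list to chelation-naïve patients.
- Give the combination one rule.
- Correct the cross-references in the same pass.

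**SAP.**
- Limit S01 to naïve patients.
- Limit S03 to ferritin-based adjustments after the allowed time (4 weeks if naïve, 3 months if pre-treated), within the permitted step and the maximum dose.
- Make S11/S12 and S17/S18 agree.
- Label the code changes as made after the interim lock, and report the PPS result under both the existing and the revised codes.

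**Cost.** This is wording only and needs no new data. Enforcing 20 mg/kg has a clinical price: NTDT patients above 4000 ng/ml stay below the 30 mg/kg that the Amendment 1 rationale describes as effective. Timing limits the gain. At Amendment 1, 132 of about 145 patients were enrolled, so a clearer starting rule could then help only about 145 − 132 = 13. After the interim lock, which follows Week 48 for all patients, it helps none. The NTDT clarification still matters for dose adjustments in patients who remain in the extension. The current SAP carries the same date (08-Apr-2021) as an addendum recorded after the interim lock, at which the primary analysis is done, so the code changes are post hoc and both PPS results are needed.

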2.4 Rationale for choice of combination drugs

Not applicable

2.5 Rationale for choice of comparators drugs

Not applicable

3 Objectives and endpoints

Objectives and related endpoints are described in [Table 3-1](#) below.

Table 3-1 Objectives and related endpoints

Objective	Endpoint	Analysis
Primary		Refer to Section 10.4
To evaluate patient preference between deferasirox FCT and deferasirox DT	Proportion of patient claimed preference of deferasirox FCT over deferasirox DT as measured by preference questionnaire at Week 48	
Secondary		Refer to Section 10.5.1
To evaluate patient preference of deferasirox FCT or deferasirox DT or previous iron chelation	Proportion of patient claimed preference of deferasirox FCT, deferasirox DT, and previous iron chelation as measured by preference questionnaire at Week 28	
To evaluate patient preference of deferasirox DT or previous iron chelation	Proportion of patient claimed preference of deferasirox DT, over previous iron chelation as measured by preference questionnaire at Week 4 and Week 24	
To evaluate the reason behind preference for deferasirox FCT or deferasirox DT	Proportion of preference reasons for deferasirox FCT over deferasirox DT as measured by preference questionnaire at Week 28 and Week 48	
To evaluate the effect of deferasirox FCT compared with deferasirox DT on patient compliance using pill count	Relative consumed pill count during deferasirox FCT (Week 25 to 48) compared with deferasirox DT (Baseline day 1 to Week 24)	
To evaluate the effect of deferasirox FCT compared with deferasirox DT or previous iron chelation on patient palatability using PRO	Absolute and relative change in domain scores of palatability questionnaire over time during deferasirox FCT (Week 28 to 48) compared with deferasirox DT (Week 4 to 24) or previous iron chelation (Screening)	
To evaluate the effect of deferasirox FCT compared with deferasirox DT or previous iron chelation on patient satisfaction using PRO	Absolute and relative change in domain scores of SICT questionnaire over time during deferasirox FCT (Week 28 to 48) compared with deferasirox DT (Week 4 to 24) or previous iron chelation (Screening)	
To evaluate the effect of deferasirox FCT compared with deferasirox DT or previous iron chelation on patient GI symptom using PRO	Absolute and relative change in domain scores of SICT questionnaire over time during deferasirox FCT (Week 28 to 48) compared with deferasirox DT (Week 4 to 24) or previous iron chelation (Screening)	

Objective	Endpoint	Analysis
To evaluate the overall safety of deferasirox FCT compared with deferasirox DT	Overall safety, as measured by frequency and severity of adverse events and changes in laboratory values of interest during deferasirox FCT (Week 25 to 48) compared with deferasirox DT (Baseline day 1 to Week 24)	
To evaluate efficacy of deferasirox (both DT and FCT) in decreasing serum ferritin levels	Absolute and relative change from baseline (Day 1) in serum ferritin on monthly basis	

4 Study design

4.1 Description of study design

This is an open-label, multicenter, single arm, phase II study aimed at collecting data on preference for iron chelation therapy in patients with transfusion-dependent thalassemia (TDT) or non-transfusion-dependent thalassemia (NTDT) throughout a 48 week treatment period.

It is a pre-requisite for the patient to provide written consent for participation in this study. This must be in place prior to performing any study-related procedures or assessments, including those described at the screening visit (please refer to [Table 7-1](#) and [Table 7-2](#)

Patients will undergo up to 4 weeks of screening and if deemed eligible, will receive deferasirox dispersible tablet (DT) formulation for 24 weeks. At the completion of 24 weeks patients will be transitioned on Week 25 to an equivalent dose of the deferasirox film coated tablet (FCT) formulation and continue treatment until Week 48 (EOT of Core Phase).

Patients can then continue deferasirox FCT formulation as per the judgment of the investigator, through an extension phase for a maximum of 12 months from the last dose of deferasirox FCT received at the end of period 2 in the Core Phase.

If one of the end of study criterion is met at any time during the study, the patient must discontinue from the study and should complete the Study Evaluation Completion (SEC - visit number 777). Please refer to [Section 4.4](#) .

Patients must be followed up for 30 days after the last dose of study drug for safety evaluation (safety follow up visit).

- Core Phase:
 - Screening phase which lasts for a maximum of 4 weeks to determine patient eligibility followed by
 - Baseline visit (day 1)
 - Period 1: deferasirox DT as 20-40 mg/kg/day dose regimen of dispersible tablet formulation for 24 weeks followed by
 - Period 2: deferasirox FCT as 14-28 mg/kg/day dose regimen of film- coated tablet for 24 weeks.
- Extension Phase:

Deferasirox FCT as 14-28 mg/kg/day dose regimen of film-coated tablet.
- PRO Validation Sub-study:
 - Patients in Egypt and Thailand may participate in this optional sub-study [sub-study protocol will only be submitted in the participating countries]

[figure not shown]
Participation in the extension phase is optional. Please refer to [Section 4.4](#) for EOS criteria.

Study treatment should be administered by the patient once per day. Patients will return to the site every 2 weeks until Week 4 (V4) and then every 4 weeks for study medication and study assessments as specified in -[Table 7-1](#) and [Table 7-2](#).

Serious adverse events, regardless of causality, occurring after the subject has provided consent until 30 days following the last administration of study treatment must be reported to the Novartis drug safety team within 24 hours of the investigator learning of its occurrence.

Patients who discontinue study treatment early before completing the study (regardless if the discontinuation occurs at core or extension phase) should be scheduled for a visit as soon as possible, at which time all of the assessments listed for SEC (visit 777) must be performed.

Figure 4-1 Study design

4.2 Switching of treatments

At the discretion of the investigator, patients can switch from deferasirox DT to deferasirox FCT at any time during Period 1 of the Core phase, and vice versa, from deferasirox FCT to deferasirox DT at any time during Period 2 of the Core phase.

This change and the rationale of the switch must be recorded in the CRF. Also the investigator must provide the preference questionnaire to the patient at the immediate next visit and then keep following the schedule of questionnaires pre-planned on [Table 7-1](#) and [Table 7-2](#) (for example; if the investigator decides to switch from deferasirox DT to deferasirox FCT at Week 12, the preference questionnaire must be provided to the patient on the next visit, Week 16, and the rest of the preference questionnaires as per regular schedule: Week 24, Week 28 and Week 48). Please refer to [14 Appendices](#) for further information on preference questionnaire completion.

The investigator can decide in the best interest of the patient to switch from one formulation to the other with the agreement of the patient if an adverse event (*defined as the appearance of (or worsening of any pre-existing) undesirable sign(s), symptom(s), or medical condition(s) that occur after patient's signed informed consent has been obtained*) grade ≥ 2 (GI symptoms, skin rash, laboratory abnormalities) occurred with deferasirox DT or deferasirox FCT.

Re-switching treatments is not allowed within each period in this study, which means that a patient cannot switch from Deferasirox DT to Deferasirox FCT and the switch back to Deferasirox DT, and viceversa (Deferasirox FCT to Deferasirox DT, and then back to Deferasirox FCT).

